### **Visit 5 (V5) – Post-Intervention Day 1**

- Administered by trained study staff or therapist/clinician:
  - Brain MRI (required)
  - Avoid/Escape Go/No-Go task
  - BDI-II, ABSI, and SBQ-ASC (self-rated questionnaire)
  - UKU Side Effect Scale
- Integrative psychotherapy session will occur with the study therapists. The participant will discuss their experience during the dose session, including their thoughts, feelings, and experiences. Integration therapy and assessment (except MRI and the cognitive task) can occur in-person or via secure videoconferencing software (i.e. WebEx). For more detailed information on the integrative therapy sessions, please refer to the therapist's manual (Yale Manual for Psilocybin-Assisted Therapy of Depression).
- The SBQ-ASC and assessment of side effects can occur in-person or remotely (via telephone/WebEx).

### **Visit 6 (V6) – Post-Intervention Day 7**

- Administered by trained study staff or therapist:
  - CGI
  - UKU Side Effect Scale
  - Self-rated questionnaires: BDI-II, ASA-A, SHAPS, RRS-10, INQ-15, ISQ-8, GAFS-8, CD-RISC 10, ABSI, AAQ-II, SBQ-ASC, CFI
- Clinician administered:
  - GRID-HAMD-17
- The self-rated questionnaires and clinical assessment (including GRID-HAMD-17, CGI and side effects) can occur in-person or remotely (via telephone/WebEx). When a participant opts to have questionnaires done remotely, they will receive the electronic version of the questionnaires by email or CAMH secure file transfer. The participant could complete the questionnaires electronically or print and fill in the questionnaires, and email (when completed directly electronically or when completed in the paper form then scanned), mail, or fax (when completed in the paper form) the completed questionnaires back to the study team. If participants choose to return the questionnaires by mail, we will provide a pre-paid postage envelope.
- Integrative psychotherapy session will occur with the study therapists. The participant will discuss their experience during the dose session including their thoughts, feelings, and experiences. Integration therapy and assessment can occur in-person or via secure videoconferencing software (i.e. WebEx). For more detailed information on the integrative therapy sessions, please refer to the therapist's manual (Yale Manual for Psilocybin-Assisted Therapy of Depression).

### **Visit 7 (V7), Visit 8 (V8) & Visit 9 (V9) – Follow-Up: Week 2, Week 4 & Week 12**

Follow-up visits occur at Weeks 2 (V7), 4 (V8), and 12 (V9) after the intervention.

*The following assessments will occur at V7:*

- Administered by trained study staff:
  - UKU Side Effect Scale
  - Self-rated questionnaires: BDI-II, ABSI and, SBQ-ASC
- Clinician administered:
  - Review of safety assessments

*The following assessments will occur at V8 and V9:*

- Administered by trained study staff:
  - CGI
  - UKU Side Effect Scale
  - Self-rated questionnaires: BDI-II, ASA-A, SHAPS, RRS-10, INQ-15, ISQ-8, GAFS-8, CD-RISC 10, ABSI, AAQ-II, WHOQOLY-4, SBQ-ASC, CFI
- Clinician administered:
  - GRID-HAMD-17
  - Review of safety assessments
- The self-rated questionnaires and clinical assessments (including GRID-HAMD-17, CGI and side effects) at V7-9 can occur in-person or remotely (via telephone/WebEx). When a participant opts to have questionnaires done remotely, they will receive the electronic version of the questionnaires by email or CAMH secure file transfer. The participant could complete the questionnaires electronically or print and fill in the questionnaires, and email (when completed directly electronically or when completed in the paper form then scanned), mail, or fax (when completed in the paper form) the completed questionnaires back to the study team. If participants choose to return the questionnaires by mail, we will provide a pre-paid postage envelope.

At V9 (or the last study visit if they withdraw from the main clinical trial earlier), participants' acceptability of the main clinical trial protocol using the custom-designed questionnaire will be assessed.

### **6.1.2.2 Outline of Study Procedures of Optional Dense Sampling Brain MRI Data Collection**

In addition to two brain MRI scans at V2 and V5 of *the main clinical trial*, the participants who opts to participate in *the optional dense sampling brain MRI data collection* will also receive brain MRI scans for

- V1 of the main clinical trial (1st scan of the sub-study; 1st scan of the 10 total scans; about 20 minutes)
- In the middle of antidepressant/antipsychotic tapering period (2nd scan of the sub-study; 2nd scan of the 10 total scans; about 20 minutes)
  - Either at the start of the 2nd week for those with 2-week washout
  - Or at the start of the 3rd week for those with 4-week washout

- One day post-V3 of the main clinical trial (3rd scan of the sub-study; 4th scan of the 10 total scans; about 20 minutes)
- V6 of the main clinical trial (4th scan of the sub-study; 6th scan of the 10 total scans; about 20 minutes)
- V7 of the main clinical trial (5th scan of the sub-study; 7th scan of the 10 total scans; about 20 minutes)
- V8 of the main clinical trial (6th scan of the sub-study; 8th scan of the 10 total scans; about 20 minutes)
- Week 8 following V5 of the main clinical trial (7th scan of the sub-study; 9th scan of the 10 total scans; about 20 minutes)
- V9 of the main clinical trial (8th scan of the sub-study; 10th scan of the 10 total scans; about 20 minutes)

At each optional MRI scan visit, the participants will complete the self-rated questionnaires of BDI-II, AAQ-II and ABSI (48 items in total). These measures will be originally collected at V6, V7 and V9 in the main clinical trial.

At V9 (or the last study visit if they withdraw from the optional dense sampling earlier), participants' acceptability of the optional dense sampling MRI protocol using the custom-designed questionnaire will be assessed.

## 6.2 Schedule of Events

### 6.2.1 Main Clinical Trial

| Procedures   | Screening Visit (V1) | Tapering Period (2-4 weeks) | Baseline Visit 2 (V2, Day -15 to Day -8) | Safety Dose (V3, Day -7) | Treatment Dose (V4, Day 0) | Study Visit 5 (V5, Day 1) | Study Visit 6 (V6, Week 1) | Study Visit 7 (V7, Week 2) | Study Visit 8 (V8, Week 4) | Study Visit 9 (V9, Week 12) |
|---|-----------------------------|--|---|---------------------------------|-----------------------------------|----------------------------------|-----------------------------------|-----------------------------------|-----------------------------------|------------------------------------|
| Location of Visit   | Clinic                      | Remote or Clinic                               | Clinic  | Clinic                          | Clinic                            | Clinic                           | Remote or Clinic                  | Remote or Clinic                  | Remote or Clinic                  | Remote or Clinic                   |
| Allowable Window  |                             | Weekly   |   | Within 7 days following V2      | Within 7-10 days following V3     | None                             | ±3 days                           | ±3 days                           | ±3 days                           | ±3 days                            |
| Informed consent  | X                           |  |   |                                 |                                   |                                  |                                   |                                   |                                   |                                    |
| Demographics  | X                           |  |   |                                 |                                   |                                  |                                   |                                   |                                   |                                    |
| Medical history   | X                           |  | X   |                                 |                                   |                                  |                                   |                                   |                                   |                                    |
| Prior/Concomitant medication review                             | X                           | X  | X   | X                               | X                                 | X                                | X                                 | X                                 | X                                 | X                                  |
| Inclusion/Exclusion Criteria Review                             | X                           | X  | X   |                                 |                                   |                                  |                                   |                                   |                                   |                                    |
| Vital signs   | X                           |  | X   | X                               | X                                 |                                  |                                   |                                   |                                   |                                    |
| Height  | X                           |  |   |                                 |                                   |                                  |                                   |                                   |                                   |                                    |
| Weight  | X                           |  |   |                                 |                                   |                                  |                                   |                                   |                                   |                                    |
| Clinical laboratory tests                           | X                           |  |   |                                 |                                   |                                  |                                   |                                   |                                   |                                    |
| EKG/ECG   | X                           |  |   |                                 |                                   |                                  |                                   |                                   |                                   |                                    |
| Urinalysis  | X                           |  |   |                                 |                                   |                                  |                                   |                                   |                                   |                                    |
| Urine drug screening  | X                           |  | X   |                                 |                                   |                                  |                                   |                                   |                                   |                                    |
| Urine Pregnancy test                                | X                           |  | X   |                                 |                                   |                                  |                                   |                                   |                                   |                                    |
| Documentation of birth control                                  | X                           |  |   |                                 |                                   |                                  |                                   |                                   |                                   |                                    |
| Preparatory/ Integrative therapy & psychoeducation  |                             |  | X   | X                               | X                                 | X                                | X                                 |                                   |                                   |                                    |

|   |   |   |   |   |   |   |   |   |   |   |
|---|---|---|---|---|---|---|---|---|---|---|
| Safety dose (10mg of psilocybin)  |   |   |   | X |   |   |   |   |   |   |
| Treatment dose (25mg of psilocybin)                                       |   |   |   |   | X |   |   |   |   |   |
| Adverse event and serious adverse event review plus UKU Side Effect Scale | X | X | X | X | X | X | X | X | X | X |
| CRF Completion  | X | X | X | X | X | X | X | X | X | X |
| 11D-ASC   |   |   |   | X | X |   |   |   |   |   |
| AAQ-II  |   |   | X |   |   |   | X |   | X | X |
| ABSI  |   |   | X |   |   | X | X | X | X | X |
| ADOS-2  | X |   |   |   |   |   |   |   |   |   |
| AQ-12   | X |   |   |   |   |   |   |   |   |   |
| ASA-A   |   |   | X |   |   |   | X |   | X | X |
| ATHF  | X |   |   |   |   |   |   |   |   |   |
| BDI-II  |   |   | X |   |   | X | X | X | X | X |
| CAT-Q   | X |   |   |   |   |   |   |   |   |   |
| CD-RISC 10  |   |   | X |   |   |   | X |   | X | X |
| CFI   |   |   | X |   |   |   | X |   | X | X |
| CGI   |   |   | X |   |   |   | X |   | X | X |
| GAFS-8  |   |   | X |   |   |   | X |   | X | X |
| GRID-HAMD-17  | X |   | X |   |   |   | X |   | X | X |
| INQ-15  |   |   | X |   |   |   | X |   | X | X |
| ISQ-8   |   |   | X |   |   |   | X |   | X | X |
| RBQ-2A  | X |   |   |   |   |   |   |   |   |   |
| RRS-10  |   |   | X |   |   |   | X |   | X | X |
| RSPM  | X |   |   |   |   |   |   |   |   |   |
| SBQ-ASC   | X | X | X |   |   | X | X | X | X | X |
| SCID-5-CV   | X |   |   |   |   |   |   |   |   |   |
| SHAPS   |   |   | X |   |   |   | X |   | X | X |
| WHOQOL-4  |   |   | X |   |   |   |   |   | X | X |

|                            |  |  |   |  |  |   |  |  |  |   |
|----------------------------|--|--|---|--|--|---|--|--|--|---|
| Acceptability              |  |  |   |  |  |   |  |  |  | X |
| Avoid/Escape Go/No-Go task |  |  | X |  |  | X |  |  |  |   |
| Brain MRI      |  |  | X |  |  | X |  |  |  |   |

1. Additional visits may be needed during the washout period to ensure adequate time for discontinuation of medication. Visits will occur on a weekly basis during this period (V1a, V1b, etc.). Review of medications and assessments for suicidality will occur in addition to other assessments at the discretion of the study investigator.
2. Baseline assessments can occur on separate days (within 7 days from safety dose) to reduce the burden on participants. These visits will be V2a, V2b etc.
3. See Section 6.0: Research Procedures for complete list of required laboratory tests to be performed.
4. For women/females and people of child-bearing age only.
5. Additional therapy visits may be scheduled at the discretion of the study therapists and/or the study investigator and therapy can occur in-person or via WebEx.
6. To be administered immediately after the acute effects of psilocybin have subsided.
7. Required for the main clinical trial design, around 45 mins

**Instruments:**

ADOS-2: Autism Diagnostic Observation Schedule; ASA-A: Anxiety Scale for Adults – Autism; ASQoL: Autism Spectrum Quality of Life Form; ATHF: Antidepressant Treatment History Form; BDI-II: Beck Depression Inventory, 2nd edition CGI: Clinical Global Impression; EKG/ECG: Electrocardiogram; GAFS-8: General Alexithymia Factor Score; GRID-HAMD: GRID-Hamilton Depression Rating Scale; MRI: Magnetic Resonance Imaging; RRS: Ruminative Response Scale; SBQ-ASC: Suicidal Behaviors Questionnaire – Autism Spectrum Conditions; SCID-5: Structured Clinical Interview for DSM-5; SHAPS: Snaith Hamilton Pleasure Scale; SRS: Social Responsiveness Scale

**6.2.2 Optional Dense Sampling Brain MRI Data Collection**

| Procedures        | Screening Visit (V1)                              | Tapering Period  (2-4 weeks) | Baseline Visit 2 (V2, Day -15 to Day -8) | Additional Visit (1 day post-V3, Day -6)  | Treatment Dose (V4, Day 0)    | Study Visit 5 (V5, Day 1) | Study Visit 6 (V6, Week 1) | Study Visit 7 (V7, Week 2) | Study Visit 8 (V8, Week 4) | Additional Visit (Week 8)  | Study Visit 9 (V9, Week 12) |
|-------------------|---|--|--|---|-------------------------------|---------------------------|----------------------------|----------------------------|----------------------------|--|-----------------------------|
| Location of Visit | Clinic  | Clinic                                   | Clinic                                   | Clinic  | Clinic                        | Clinic                    | Clinic                     | Clinic                     | Clinic                     | Clinic                                 | Clinic                      |
| Allowable Window  | Within 7 days following Screening MRI of V1 Visit | Starting immediately following MRI of V1 |  | Within 1 days following Safety Dose                   | Within 7-10 days following V3 | None                      | ±3 days                    | ±3 days                    | ±3 days                    | ±3 days                                | ±3 days                     |
| CRF Completion    | X   | X  | X  | X   | X                             | X                         | X                          | X                          | X                          | X                                      | X                           |
| Brain MRI         | X                                     | X                            | X                            | X   |                               | X             | X              | X              | X              | X                          | X               |
| AAQ-II            | X   | X  | X  | X   |                               | X                         | X                          | X                          | X                          | X                                      | X                           |
| ABSI              | X   | X  | X  | X   |                               | X                         | X                          | X                          | X                          | X                                      | X                           |
| BDI-II            | X   | X  | X  | X   |                               | X                         | X                          | X                          | X                          | X                                      | X                           |
| Acceptability     |   |  |  |   |                               |                           |                            |                            |                            |  | X                           |

|   |   |   |   |   |   |   |   |   |   |   |   |
|---|---|---|---|---|---|---|---|---|---|---|---|
| Adverse event and serious adverse event review plus the UKU Side Effect Scale | X | X | X | X | X | X | X | X | X | X | X |
|---|---|---|---|---|---|---|---|---|---|---|---|

1. In the middle of either 2-week or 4-week washout period.
2. The additional visit for the optional dense sampling brain MRI data collection.
3. The additional brain MRI scans for the optional dense sampling brain MRI data collection.
4. The original brain MRI scans for the main clinical trial design.

## 7.0 STATISTICAL PLAN

### 7.1 Sample Size Determination

The proposed sample size of *the main clinical trial* is determined based on the recommendations for pilot trials (Whitehead et al., 2016) and is also a sample size adopted by earlier pilot trials on psilocybin (Carhart-Harris et al., 2016). For the main trial designed with 90% power and two-sided 5% significance, our sample size can detect an effect size (ES) of 0.76 (Cohen's d). We will be able to obtain reasonably reliable estimates on feasibility measures including recruitment (margin of error 15.5%) and retention rate (margin of error 13.1%) and tolerability (margin of error 10.1%). An fMRI study in healthy volunteers reports a very large psilocybin effect size in changes of functional connectivity at Week 1 (ES 1.73) (McCulloch et al., 2022). A meta-analysis of published psilocybin trials reports a large antidepressant effect size in neurotypical populations (ES 0.8) (Galvão-Coelho et al., 2021). Altogether, the proposed sample size of *the main clinical trial* appears to have sufficient power to detect the expected effects.

The proposed sample size of *the optional dense sampling brain MRI data collection* is determined based on a pilot study with the similar dense sampling neuroimaging approach happening at the CAMH (titled "Deriving Everyday Effects of Psychosis - Pilot (DEEP-Pi)"). The Midnight Scan Club dataset, representing the first multi-person deep phenotyping study in healthy individuals, also included a sample of 10 individuals, suggesting that for repeated scanning approaches a sample size of 10 is adequate (Gratton et al., 2018). Nonetheless, we acknowledge this rationale of the sample size decision is arbitrary and recognize this optional dense sampling approach is preliminary and novel.

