## **2.0 CLINICAL TRIAL OBJECTIVES**

### **2.1 Primary Objective of Main Clinical Trial**

To investigate the feasibility, tolerability, and safety of administering psilocybin in autistic adults with TRD.

Hypothesis 1a (feasibility): We will be able to recruit 20 participants within 21 months with retention >90%.

Hypothesis 1b (tolerability and safety): Adverse events (tolerability) and serious adverse events (safety) will be similar to those reported in the literature on classic serotonergic psychedelics in neurotypical populations.

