## **2.3 Exploratory Objective of Main Clinical Trial**

To evaluate a signal of antidepressant and other beneficial effects of psilocybin for TRD in adults with autism.

Hypothesis: While this trial is not powered to determine antidepressant efficacy, we expect an antidepressant effect size to be close to (or comparable to) that reported in neurotypical depression.

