### 4.2 Participant Recruitment and Screening

The target sample size of *the main clinical trial* is 20 participants (N=20, 10 male, 10 female) diagnosed with autism and treatment-resistant depression. The study will take place at a single site: the Centre for Addiction and Mental Health (CAMH) in Toronto, Ontario. The target sample size of *the optional dense sampling brain MRI data collection* is 10 out of the 20 participants that have been enrolled in *the main clinical trial*, regardless of the sex.

The source of participants in this study will come from CAMH outpatient units and external healthcare providers. Clinicians at CAMH may identify potential research participants and obtain verbal permission from these potential participants for a member of the research

team to approach them. Potential participants that are interested in participating in the study will be prescreened by a member of the study team, as outlined below.

CLEARRR will be used to recruit participants for this clinical trial. All new referrals will be reviewed by the CLEARRR coordinator and CLEARRR physician for eligibility to participate using minimal inclusion/exclusion criteria outlined. Once a patient is identified as potentially suitable for the clinical trial, the attending physician will be notified via outlook calendar invite or email that their patient may be eligible for the clinical trial. The attending physician will decide whether research is appropriate for the patient and if so, they will ask the patient for consent to be contacted regarding the clinical trial. If the patient provides verbal consent to be contacted to receive more information about the clinical trial, the physician will connect the patient with the CLEARRR coordinator or research team who will further explain the clinical trial. No personal health information (PHI) will be given to the research team prior to obtaining the patient's consent.

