## **4.7 Participant Withdrawal Criteria**

### **4.7.1 When and How to Withdraw Participants**

Participants are free to withdraw from participation in the clinical trial at any time.

An investigator may discontinue or withdraw a participant from the clinical trial for the following reasons:

- Pregnancy or if participants cease effective contraception;
- Significant study intervention non-compliance;
- If any adverse event (AE), laboratory abnormality, or other medical condition or situation occurs such that continued participation in the clinical trial would not be in the best interest of the participant; or
- Disease progression which requires discontinuation of the study intervention;
- If the participant meets an exclusion criterion (either newly developed or not previously recognized) that precludes further study participation.

Notably, even if participants cannot complete a post-treatment brain MRI scan (V5) of *the main clinical trial design* or cannot complete any of brain MRI scans of *the optional dense sampling brain MRI data collection* (either for the personal reasons or for an exclusion criterion for the MRI scan), they will not be discontinued/withdrawn from the trial by an investigator.

The reason for participant discontinuation or withdrawal from the study will be recorded within the participant's research record, and/or health record at CAMH.

Participants that are withdrawn from the study will be replaced using the same recruitment methods as outlined in Section 4.2: Participant Recruitment and Screening. The aim is to have 20 participants who complete the study.

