### 7.2 Statistical Methods

For Primary Aim (safety/feasibility) of *the main clinical trial*, all participants entering the psilocybin sessions (V3/3) will be included in the analysis of the safety profile and tolerability. Participants completing the two time points of pre- and post-treatment MRI and cognitive tests will be included in the analysis for the neuroscience objective. Participants who at least complete the follow-up at Week 1 (V6) will be included in the final analysis for the exploratory aim of clinical effects, regardless of whether they complete the full protocol. This approach is consistent with the intention-to-treat principle. A paired t-test will be used to investigate the pre- to post-treatment brain/cognitive metrics and symptom changes of *the main clinical trial*. Exploratory analyses will be performed to determine predictors of response including baseline individual features, using logistic regression. Safety profiles will be described by the percentage of each adverse effect.

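### The retention and tolerability margins of error in Protocol 7.1 have no stated basis and understate the downside uncertainty, and the power sentence there conflicts with 2.3

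*Protocol*

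**What the plan says.** Protocol 7.1 bases the sample size on recommendations for pilot trials and on earlier psilocybin pilots. It then supports the choice with precision figures for the feasibility and tolerability measures: "recruitment (margin of error 15.5%) and retention rate (margin of error 13.1%) and tolerability (margin of error 10.1" (per cent). No assumed proportion, denominator, confidence level or interval method accompanies them.

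The related inputs are elsewhere in the protocol:

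- Section 4.2 sets the target: "20 participants (N=20, 10 male, 10 female) diagnosed with autism and treatment-resistant depression".
- Section 2.1, Hypothesis 1a: "We will be able to recruit 20 participants within 21 months with retention >90" per cent.
- Section 7.2 defines the tolerability set without a number: "all participants entering the psilocybin sessions (V3/3) will be included in the analysis of the safety profile and tolerability".
- Section 4.7.1 replaces withdrawn participants: "The aim is to have 20 participants who complete the study".

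On power, 7.1 begins "For the main trial designed with 90% power and two-sided 5% significance" and gives a detectable effect of 0.76. It cites an imaging effect of 1.73 and an antidepressant effect of 0.8, and concludes that the sample "appears to have sufficient power to detect the expected effects". Section 2.3 says: "While this trial is not powered to determine antidepressant efficacy".

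**The concern.** Retention and tolerability are expected to be high and the group is about 20 people. In that setting a symmetric normal-approximation margin is unreliable: it can pass 100% at the top and stop well short of the plausible values at the bottom. The lower side is the one that matters for a feasibility and tolerability study, because the reader wants to know how poor the true rate could be given a good observed one.

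These are the only precision figures the protocol prints for its primary aims. A reader who takes plus or minus 13 and plus or minus 10 points at face value would judge Hypotheses 1a and 1b on better evidence than 20 people can give. Without proportions and denominators, nobody can check the figures or carry them forward to a larger trial.

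Separately, 7.1 and 2.3 give a reader opposite messages about the antidepressant outcome.

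**Working it through.** **Inputs.** N=20 (4.2); retention 90%, the threshold in Hypothesis 1a (2.1); stated margins 15.5, 13.1 and 10.1 (7.1). No confidence level is given for the margins, so 95% is assumed.

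**Step 1: reproduce the stated margins.** Wald half-width = 1.96 × √(p(1−p)/n).

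- Retention, p=0.90, n=20: 1.96 × √(0.09/20) = 1.96 × 0.0671 = 13.15% (13.148 before rounding; stated 13.1). Both inputs are the protocol's own.
- Tolerability: the protocol gives no proportion. With p=0.95, n=18: 1.96 × √(0.0475/18) = 10.07%. At n=20 throughout, 10.1 needs p=0.944; the observable 19/20 gives 9.55%.
- Recruitment: p=0.50, n=40 gives 1.96 × √(0.25/40) = 15.49%. So does p=0.75, n=30: 1.96 × √(0.1875/30) = 15.49%. At n=20 it needs p=0.853; 17/20 gives 15.65%.

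Only the retention margin can be tied to inputs that the protocol states. The other two sets of inputs are inferences.

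**Step 2: what the margins imply.**

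- Retention: 90 ± 13.1 gives 76.9% to 103.1%.
- Tolerability (p=0.95, n=18): 95 ± 10.1 gives 84.9% to 105.1%. At n=20, p=0.944: 94.4 + 10.1 = 104.5%, still above 100%.
- Recruitment: 34.5% to 65.5% (n=40) or 59.5% to 90.5% (n=30), both inside 0 to 100%.

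**Step 3: limits that hold at this sample size.** Clopper-Pearson limits for k of n are the 0.025 quantile of Beta(k, n−k+1) and the 0.975 quantile of Beta(k+1, n−k). Wilson limits are [p + z²/2n ± z√(p(1−p)/n + z²/4n²)] / (1 + z²/n), with z=1.96.

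| Quantity | Observed | Clopper-Pearson 95% | Wilson 95% | Downside, points | Stated |
|---|---|---|---|---|---|
| Retention | 18/20 = 90% | 68.3–98.8% | 69.9–97.2% | 21.7 / 20.1 | 13.1 |
| Tolerability | 19/20 = 95% | 75.1–99.9% | 76.4–99.1% | 19.9 / 18.6 | 10.1 |
| Tolerability | 17/18 = 94.4% | 72.7–99.9% | 74.2–99.0% | 21.7 / 20.2 | 10.1 |
| Recruitment | 20/40 = 50% | 33.8–66.2% | 35.2–64.8% | 16.2 / 14.8 | 15.5 |

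For retention the shortfall is 21.7 − 13.1 = 8.6 points (exact) or 20.1 − 13.1 = 7.0 (Wilson). For tolerability at 19/20 it is 9.8 (exact) or 8.5 (Wilson). The nominal 95% Wald interval covers the truth about 88% of the time at p=0.90, n=20.

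**Step 4: effect of replacement.** Under 4.7.1 the retention denominator can exceed 20. For example, 20 completers of 22 gives a Wald half-width of 12.0 points, against an exact interval of 70.8% to 98.9%. The downside is 90.9 − 70.8 = 20.1 points, so the fault remains.

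**Step 5: the power statement.** A paired t-test with 20 pairs, two-sided 5% and 90% power detects a standardised mean change of 0.764, so the stated 0.76 is correct for 20 analysable pairs. The text does not state that condition. Section 4.7.1 keeps participants who miss the V5 scan, while 7.2 analyses imaging only in those with both scans. The closing sentence of 7.1 rests on the imaging effect of 1.73 and the antidepressant effect of 0.8 together; 2.3 disclaims power for the second.

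**The case against.** **The inputs are guesses.** This stands in part. Other pairs fit: p=0.80, n=36 also gives 13.1, and p=0.90, n=34 also gives 10.1. A reader might infer that the three margins come from three different sample sizes (40, 20 and 18). The documents do not establish that: several combinations fit each figure, and a common n=20 is possible with unrounded proportions. The retention match is different, because N=20 and 90% are both in the protocol. For retention and tolerability, no reading with 20 or fewer participants removes the fault.

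**Not every margin fails.** Correct. A reader might infer that all three run past 100%. Recruitment does not, and against 20/40 its exact half-width is 16.2, close to 15.5. Nor can one say that a percentage cannot describe recruitment: 3.2 names recruitment and retention rates as endpoints. The protocol simply does not say which proportion is meant, while Hypothesis 1a is a count over time.

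**Clopper-Pearson is conservative, and the choice of interval can be left to the analysis plan.** Also fair, which is why Wilson limits are shown. They narrow the gap by one or two points but do not close it. The defect is in a printed figure, not in the absence of a chosen method.

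**The sample does not depend on these margins.** True. It rests on pilot-trial recommendations and precedent, and no decision rule in the protocol uses the margins.

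**Power may fall short if only 18 pairs are available.** This is tempting but not supported. Withdrawals are replaced with the aim of 20 completers. A missed V5 scan reduces only the imaging set, whose cited effect is 1.73. Even with 18 pairs, power at 0.8 would be 89.2%.

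**Detecting a pre-post change differs from determining efficacy, so 7.1 and 2.3 can coexist.** That may be the intent. However, 7.1 cites the antidepressant effect size without that distinction, so the two sections need reconciling.

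**Conclusion.** The concern holds for two of the three margins and for the power sentence. With 18 of 20 retained, the downside is 20 to 22 points rather than 13.1. With tolerability of about 95% in about 20 people, it is about 19 to 22 points rather than 10.1. The margins are therefore short by about 7 to 9 points for retention and about 8 to 12 for tolerability, depending on the interval method and the assumed count.

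The retention result uses the protocol's own N and threshold and assumes 95% confidence. (Hypothesis 1a asks for more than 90%, so 18/20 would itself just miss it; the count is used because it reproduces the stated margin.) The tolerability result also assumes a proportion that the protocol does not give. The recruitment margin needs a definition, not a correction of size. The conflict between 7.1 and 2.3 is one of wording and needs no calculation.

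This should be fixed because a stated figure for the primary aims is misleading. It is not critical: the sample size, conduct and planned analyses would not change.

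**What to change.** Rewrite the precision and power sentences of Protocol 7.1:

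- For each margin, state the assumed proportion, the denominator (allowing for replacement under 4.7.1 and, for tolerability, the analysis set in 7.2), the confidence level and the method.
- Replace the symmetric retention and tolerability margins with exact or Wilson limits. For illustration, 18/20 gives 68.3% to 98.8% exact or 69.9% to 97.2% Wilson. Give the tolerability limits for whatever proportion and denominator the investigators intend.
- Say which recruitment quantity the 15.5% describes. If it is the target of 20 in 21 months, give a rate: 20/21 = 0.95 per month, with an exact Poisson 95% interval of 0.58 to 1.47.
- State that 0.76 assumes 20 analysable pairs.
- Limit the claim of sufficient power to the paired imaging change, in line with 2.3.

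The cost is one rewritten paragraph and less favourable stated precision. No participants or procedures are added.
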